## 6 TREATMENT MODIFICATIONS

Subjects enrolled in this study will be evaluated clinically and with standard laboratory tests before and at regular intervals during their participation in this study as specified in Section 7.

Subjects will be evaluated for adverse events (all grades), serious adverse events, and adverse events requiring protocol therapy interruption or discontinuation at each study visit for the duration of their participation in the treatment phase of the study.

This study will utilize the CTCAE (NCI Common Terminology Criteria for Adverse Events) v4 for toxicity and Serious Adverse Event reporting. A copy of the CTCAE v4 can be downloaded from the CTEP home page (<http://ctep.cancer.gov>). All appropriate treatment areas should have access to a copy of the CTCAE v4.

### 6.1 Treatment-Limiting Adverse Events

A treatment-limiting adverse event is any adverse event related to protocol therapy experienced during the study resulting in treatment termination.

### 6.2 General Treatment Modification Considerations

- If multiple toxicities are experienced, treatment modifications will be based on the toxicity requiring the largest dose reduction.

#### 6.2.1 Modifications for Androgen Deprivation Therapy (ADT) and Bicalutamide

- Delay of up to 7 days in administering the scheduled dose of LHRH agonist or antagonist is allowed
- Missed doses of bicalutamide are to be omitted rather than made up.

##### 6.2.1.1 Modifications for Hematologic Toxicity:

Use of granulocyte colony stimulating factors is not permitted.

### 6.2.1.2 Modifications for Non-Hematologic Toxicity:

#### Diarrhea:

The major toxic effect of bicalutamide is moderate diarrhea which is rarely severe (exclusion of other causes of diarrhea should be considered in severe cases). The modifications for toxicity related to diarrhea will be as follows:

- Grade  $\geq 3$  diarrhea, permanently discontinue bicalutamide
- Grade 2 diarrhea, treat symptomatically with anti-diarrhea drugs.
- Grade 2 diarrhea unresponsive to symptomatic treatment- hold bicalutamide until diarrhea resolves to  $\leq$  Grade 1.

In case of any diarrhea  $\geq$  Grade 1, the following tests are recommended at the discretion of the site investigator as clinically indicated:

- WBC in stools
- Stool cultures
- Clostridium difficile titers
- Further testing will be at the discretion of the site investigator

#### Abnormal Liver Function Tests (SGOT/AST, SGPT/ALT, Bilirubin):

- Grade  $\geq 3$ , permanently discontinue bicalutamide
- Grade 2 toxicity
  - Hold bicalutamide and recheck liver function tests weekly until LFTs are normal (Grade 0). LFTs may be performed more frequently at the discretion of the treating physician.
  - Hepatitis screening (A, B, C) is recommended in cases of abnormal LFTs which could be consistent with infectious hepatitis.
  - Restart bicalutamide when LFTs return to normal. If the toxicity (Grade  $\geq 2$ ) recurs or if the subject requires a delay greater than 28 days, discontinue bicalutamide. Subjects will remain on protocol therapy with ADT and, if applicable, radium-223 dichloride.
- Symptoms such as flatulence, bloating and mild "gas pains" should not result in changes in bicalutamide, ADT or radium treatment. Symptomatic treatment should be employed with antacids, simethicone, etc.
- Asymptomatic Grade 3 or 4 laboratory findings, which are not considered clinically significant, may not require dose modification (i.e., dose hold). The decision to hold the dose should be based on the site investigator's clinical judgment.
- For any other Grade 3-4 adverse events, hold bicalutamide; wait until adverse event has resolved to Grade  $\leq 1$ , and then restart bicalutamide.

### 6.2.2 Modifications for Radium-223 dichloride

- Delay of up to 8 weeks (56 days) is allowed for radium-223 dichloride doses if necessitated by inadequacy of hematologic parameters or drug non-availability or necessary time interval between 2 consecutive radium-223 dichloride doses.
- A delay of 7 days is allowed for scheduling factors. There must be a minimum of 25 days between consecutive radium-223 dichloride doses.

- Every effort should be made to administer the full dosing regimen of Radium-223 dichloride. Adjustment of dose is not permitted.
- Study visits during the treatment period should occur at 28-day intervals. Dosing delays may be instituted under the following circumstances listed below.

#### **6.2.2.1 Modifications for Hematologic Toxicity:**

The following hematologic criteria must be met within 3 days prior to first dose of Radium 223:

- ANC  $\geq 1.5$  K/ mm^3
- Platelets  $\geq 100$  K/mm^3
- Hemoglobin  $\geq 8$  g/dL (80 g/L) without PRBC transfusion

The following hematologic criteria must be met within 3 days prior to administration of remaining doses:

- ANC  $\geq 1.0$  K/ mm^3
- Platelets  $\geq 50$  K/mm^3
- Hemoglobin  $\geq 8$  g/dL (80 g/L) with or without PRBC transfusion

If the hematologic parameters listed above are not met:

- Radium-223 dichloride will be held.
- Complete blood counts (CBC) will be measured weekly. Once the counts recover, radium-223 dichloride may resume at the same dose level.
- ADT and bicalutamide will continue without interruption.
- If there is no recovery to these values within 8 weeks after the last administration of radium-223 dichloride, despite receiving supportive care including blood transfusions as clinically indicated, further treatment with radium-223 dichloride will be discontinued. ADT and bicalutamide can continue and the subject will remain on study.

#### **6.2.2.2 Modifications for Non-Hematologic Toxicity:**

For Grade 4 toxicity possibly attributed to radium-223 dichloride

- Discontinue radium-223 dichloride

For Grade  $\geq 2$  toxicity attributable to radium-223 dichloride

- Radium-223 dichloride will be held until the toxicity has resolved to  $\leq$  Grade 1 or baseline.
- Supportive care should be instituted as clinically indicated.
- Once the toxicity resolves, radium-223 dichloride may resume at the same dose level.
- ADT and bicalutamide will continue without interruption.

If there is no recovery to these values within 8 weeks (56 days) after the last administration of radium-223 dichloride, despite receiving supportive care including blood transfusions as clinically indicated, further treatment with radium-223 dichloride will be discontinued. ADT and bicalutamide can continue and the subject will remain on study.

-

## 7 STUDY CALENDAR & EVALUATIONS

Early Induction Subjects = Have started ADT prior to being screened for study.

Late Induction Subjects = Have NOT started ADT prior to being screened for this study

Study Day  Induction and Post Induction Cycles = 28 days (4 weeks)  Maintenance Cycles = 84 days (12 weeks)	Screening (0 - 28 days) 	Induction Cycle 1 	Induction Cycles 2-7	Post Induction Cycle 8	Post Induction Cycles 9-12	Maintenance Cycle 13	Maintenance Cycles 14-16 	Maintenance Cycle 17	End of Treatment and Follow up 	
		Day 1	Day 1 (±3)	Day 1 (±7)	Day 1 (±7)	Day 1 (±7)	Day 1 (±14)	Day 28 (±7)	Day 1	
REQUIRED ASSESSMENTS										
Informed Consent	X									
Medical History and Diagnosis/Staging	X									
Physical examination 	X	X	X	X		X		X		
Vital signs including BP, weight, height (screening ONLY) and ECOG PS	X	X	X	X		X		X		
CBC with diff and platelet 	X	X 	X	X		X		X		
CMP, Mag, and Phos. 	X	X 	X	X		X		X		
Alk Phos, PSA 	X	X 	X	X	X	X	X	X	X	
Testosterone 	X	X 		X		X				
AEs & concomitant medications 	X	X	X	X	X	X	X	X	X	
BPI (short form), WHO ladder 		X 	X 	X						
DISEASE ASSESSMENT										
CT or MRI abdomen/pelvis 	X			X		X		X		
Chest X-ray or CT chest if clinically indicated 	X			X		X		X		
CT or MRI Brain if clinically indicated 	X			X		X		X		
Bone Scan 	X			X		X				
DEXA scan 	X					X				
TREATMENT EXPOSURE										
Arm A (Control)										
LHRH agonist/antagonist + Bicalutamide		X	—————→							
Arm B (Experimental)										
LHRH agonist/antagonist + Bicalutamide		X	—————→							
Radium-223 dichloride			X							

Study Day	Screening (0 - 28 days) 	Induction Cycle 1 	Induction Cycles 2-7	Post Induction Cycle 8	Post Induction Cycles 9-12	Maintenance Cycle 13	Maintenance Cycles 14-16 	Maintenance Cycle 17	End of Treatment and Follow up 
Induction and Post Induction Cycles = 28 days (4 weeks)									
Maintenance Cycles = 84 days (12 weeks)		Day 1	Day 1 (±3)	Day 1 (±7)	Day 1 (±7)	Day 1 (±7)	Day 1 (±14)	Day 28 (±7)	Day 1
CORRELATIVE STUDIES									
Serum for Bone Turnover Markers 		X 	X 						X 
Circulating Tumor Cells (CTCs) 		X 	X 						X 
BANKING SAMPLES									
Whole Blood 		X 	X 						X 
Serum and plasma 		X 	X 						X 
FOLLOW UP									
Survival									X
Secondary Malignancies									X

**Footnotes: Please NOTE: unless otherwise specified, all testing will be performed in BOTH arms.**

- NOTE:** Early induction subjects will have initiated ADT prior to registration. Results of screening procedures should be obtained through medical records if available including start date ADT therapy.
- Close monitoring for fractures should be done during the physical exam. If a fracture is suspected, radiological exams should be performed per clinical guidelines. Subjects should be encouraged to contact the site investigator for any new onset pain or increase in pain in sites of known bone disease.
- CBC w/diff and platelet to include: WBC with differential and platelets, hemoglobin and hematocrit. Additional monitoring of CBC w/diff and platelet per site investigator's discretion based on subject clinical status. CMP blood chemistries to include: sodium, potassium, chloride, bicarbonate, blood urea nitrogen (BUN), serum creatinine, glucose, calcium, total protein, albumin, AST, ALT, alkaline phosphatase, total bilirubin. Magnesium and phosphorus to be included.
- PSA, Alk Phos to be assessed Cycle 1 Day 1 (late induction group) or Cycle 2 Day 1 (early induction group). Subjects will be followed for PSA and Alk Phos every month for a total of 1 year from randomization then every 12 weeks (± 14 days) for the next year (2 years from randomization). If a subject withdraws consent, he is deemed "off study" and will NOT be followed further.
- Testosterone (serum) will be measured on Cycle 1 Day 1 (for late induction group only), Cycle 8 Day 1 (both early and late induction groups) and after 12 months of ADT. For early induction subjects, a testosterone value prior to initiation of ADT should be obtained via medical records, if available. If the result is not available, subjects are not ineligible for study.
- AE and concomitant medication assessment: AE assessment should include a review of any symptoms the subject may be experiencing. In addition, the subject should be assessed for secondary malignancies. Concomitant medication review will include all medications the subject is taking.
- Pain assessment with BPI (short form) and assessment of analgesic use with WHO ladder scale will be performed at 3 time-points: Cycle 1 Day 1 (late induction group) or Cycle 2 Day 1 (early induction group), on Cycle 4 Day 1 and Cycle 8 Day 1.
- CT and MRI scans if clinically indicated can be performed with or without intravenous contrast as per institutional guidelines at screening, C8D1, C13D1 and C17D28 (a window of ± 7 days for all scans is allowed). DEXA scan will be performed at screening and after completion of 1 year of treatment. CT or Brain MRI: Brain imaging studies are not required for eligibility if the subject has no neurologic signs or symptoms suggestive of brain metastasis. Subjects

with neurological symptoms are recommended to undergo a head CT scan (with or without intravenous contrast) or brain MRI (with or without intravenous contrast) to exclude brain metastasis. If brain imaging studies are performed, they must be negative for CNS disease. Skull bone involvement without neurological impact by prostate cancer is allowed. A bone scan will be performed at baseline, C8D1 and after completion of 1 year of treatment.

9. All subjects will receive androgen deprivation therapy with a LHRH agonist (any LHRH agonist such as leuprolide acetate or goserelin acetate is acceptable) or a LHRH antagonist (degarelix) or bilateral orchiectomy per the treating physician. Androgen Deprivation therapy with LHRH agonist or LHRH antagonist will be given continuously.
10. MANDATORY: Serum submission for Bone Turnover Markers: Pre-Dose Cycle 1 Day 1 (late induction group) and thereafter on Day 1 of each cycle during the remaining 6 months of protocol specified therapy and at End of Treatment (both induction groups). CTCs: For following time points only: C1D1 (late induction group only); C2D1 (early induction group only); C4D1; EOT visit. CTCs will be collected for all subjects (n = 204). See Correlative Laboratory Manual (CLM) for collection, labeling and shipping instructions.
11. MANDATORY: Whole blood for banking is to be collected pre dose Cycle 1 Day 1 (late induction group) or pre dose Cycle 2 Day 1 (early induction group) and at EOT. Serum and plasma are to be collected at Pre-Treatment Cycle 1 Day 1 (late induction group) or Cycle 2 Day 1 (early induction group) and at EOT. See CLM for collection, labeling, processing and shipping instructions.
12. For late induction subjects, Cycle 1 Day 1 will occur after screening and upon completion of eligibility. C1D1 lab testing need not be repeated if completed within 7 days of starting protocol therapy. For early induction subjects, C1D1 occurs prior to screening; documentation of initiation of ADT (C1D1) should occur after review of the subject chart and completion of eligibility.
13. For maintenance Cycles 14-17, subjects will continue to be followed every 12 weeks for alkaline phosphatase, PSA values and AE/concomitant medication updates, initiation of new anti-cancer therapy and occurrence of secondary malignancies. This information may be obtained via local treating physician medical records.
14. The end of treatment/follow up column will be utilized for subjects that come off protocol therapy (both Arm A and Arm B) for toxicity or progression. If this occurs, subjects should have an end of treatment visit 30 days ( $\pm$  7 days) after discontinuation of protocol therapy. Subjects will then continue to be followed every 3 months for a total of 2 years from the date of randomization. If a subject withdraws consent, he is deemed "off study" and will NOT be followed further. Follow up may occur via phone call, email or other communication. If available by medical record review, alk phos, PSA, AE/concomitant medication should be obtained.

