### 7.7 Maintenance: Cycle 13 Day 1; 12 months from ADT initiation ( $\pm 7$ days):

- Clinical: Physical examination including BP measurement, weight, ECOG performance status, assessment of adverse events and concomitant medications. Close monitoring for fractures should be done during all physical exams. If a fracture is suspected radiological exams should be performed per clinical guidelines. Subjects should be encouraged to contact the site investigator for any new onset pain or increase in pain in sites of known bone disease.
- Laboratory Testing:
  - CMP to include sodium, potassium, chloride, bicarbonate, blood urea nitrogen (BUN), serum creatinine, glucose, calcium, total protein, albumin, AST, ALT, alkaline phosphatase, total bilirubin, magnesium, phosphorus
  - CBC (WBC with differential and platelet count, hemoglobin and hematocrit)
  - Serum testosterone
  - Alkaline phosphatase
  - PSA
- Imaging:
  - CT or MRI abdomen/pelvis
  - DEXA scan
  - Bone Scan
  - Chest x-ray or Chest CT if clinically indicated

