### 7.8 Maintenance Cycles 14-16 Day 1 ( $\pm 14$ days)

**NOTE:** ADT may continue for up to 2 years from randomization. Maintenance Cycles will = 84 days/12 weeks.

- Laboratory tests:
  - PSA
  - Alkaline phosphatase
- Assessment of adverse events and concomitant medications. This may be done via email, phone call or medical record review

### 7.9 Maintenance Cycle 17 Day 28

- Physical examination. Close monitoring for fractures should be done during all physical exams. If a fracture is suspected radiological exams should be performed per clinical guidelines. Subjects should be encouraged to contact the site investigator for any new onset pain or increase in pain in sites of known bone disease.
- Vital signs including BP measurement, weight, ECOG performance status
- Assessment of adverse events and concomitant medications.
- Laboratory Testing:
  - CMP to include sodium, potassium, chloride, bicarbonate, blood urea nitrogen (BUN), serum creatinine, glucose, calcium, total protein, albumin, AST, ALT, alkaline phosphatase, total bilirubin. Including magnesium, phosphorus
  - CBC (WBC with differential and platelet count, hemoglobin and hematocrit)  
Additional monitoring of CBC w/diff and platelet per site investigator's discretion based on subject clinical status
  - Alkaline phosphatase
  - PSA

- Imaging:
  - CT or MRI abdomen/pelvis
  - Chest x-ray or Chest CT if clinically indicated

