### 7.10 End of Treatment (EOT) and Follow Up

The end of treatment/follow up column will be utilized for subjects that come off protocol therapy (radium-223 dichloride if randomized to that Arm and ADT) for toxicity or progression. If this occurs, subjects should have an end of treatment visit 30 days ( $\pm$  7 days) after discontinuation of protocol therapy. Subjects will then continue to be followed every 3 months for a total of 2 years from the date of randomization. Follow up may occur via phone call, email or other communication. If available by medical record review, alk phos, PSA, AE/concomitant medication should be obtained. Testing to be done at the EOT visit:

- Circulating tumor cell's (CTCs)
- Serum bone turnover markers
- Banking Samples: serum, plasma
- Alkaline phosphatase
- PSA

If a subject withdraws consent, he is deemed **“off study”**. “Off study” subjects will not be followed further.

A subject will be discontinued from the protocol specified therapy under the following circumstances:

- If there is evidence of radiologic disease progression or symptomatic deterioration despite castration range serum testosterone level ( $< 50$  ng/dL). Such subjects can go on to other treatment outside the study as clinically indicated including continuation or initiation of radium-223 dichloride therapy. They will remain on follow-up portion of the study for a total of 2 years from the date of randomization.
- If there is development of castration-resistant prostate cancer by PSA criteria in conjunction with castration range serum testosterone level ( $< 50$  ng/dL). Castration resistant prostate cancer is defined as two consecutive increases in PSA over the nadir PSA, at least two weeks apart **AND** an absolute increase of at least 2 ng/mL from the nadir PSA (or from baseline PSA if there was no drop in PSA after starting treatment). Discontinuation of bicalutamide may be attempted at the investigator's discretion in such cases and would NOT constitute going “off treatment”. If no response to bicalutamide discontinuation, such subjects may receive other treatment outside the study as clinically indicated including continuation or initiation of radium-223 dichloride therapy. They will remain on follow-up portion of the study for a total of 2 years from the date of randomization.

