**8. CRITERIA FOR DISEASE EVALUATION AND ENDPOINT DEFINITIONS**  
RECIST 1.1 criteria will apply to only soft tissue lesions. PCWG2 criteria will apply to bone lesions and PSA values.

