#### **8.1.2 Non-measurable disease**

All other lesions (or sites of disease), including small lesions (longest diameter < 1.0 cm or pathologic lymph nodes with  $\geq 1.0$  cm to <1.5 cm short axis), are considered non-measurable disease. Bone lesions, leptomeningeal disease, ascites, pleural/pericardial effusions, lymphangitis cutis/pulmonitis, inflammatory breast disease, and abdominal masses (not followed by CT or MRI), are considered non-measurable, as are previously radiated lesions that have not progressed.

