## 8.2 Progression Criteria

**8.2.1 PSA progression** is defined by two consecutive increases in PSA over the nadir PSA, at least two weeks apart AND an absolute increase of at least 2 ng/mL from the nadir PSA (or from baseline PSA if there was no drop in PSA after starting treatment).

**8.2.2 Radiographic Skeletal progression on bone scan** is defined as 2 or more new lesions on radionuclide bone scans (PCWG2 criteria). Should two or more new bone lesions be evident at the first imaging assessment (at end of protocol specified therapy), two or more additional new lesions must be evident on a confirmatory assessment at least 6 weeks later.

A bone scan may be ordered at the discretion of the treating physician within the first 7 months of protocol treatment for symptoms e.g. bone pain. If new bone lesions appear in the absence of a rising PSA within the first 7 months of protocol treatment, the site investigator at the institution must consult the sponsor-investigator (via the HCRN Project Manager) to discuss the possibility of tumor flare.

For bone disease documented on bone scan only, increased uptake does not constitute unequivocal progression. However, increase in the soft tissue component of a lesion as measured by CT or MRI would constitute progression.

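### The 140 events and 90% power in 12.1 assume assessment to month 48, but scheduled imaging ends at C17D28; the plan as written supports about 117 to 122 events and power of about 0.86 to 0.87

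*Combined protocol and SAP*

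**What the plan says.** **Power (12.1).** 140 events for 90% power at a hazard ratio of 0.632, one-sided alpha 0.10. Medians are 12 and 19 months, exponential, with 10% yearly dropout, 24 months of accrual, 48 months of study, and 68 and 136 subjects.

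**Follow-up.** Section 7.10, on subjects who come off therapy: "Subjects will then continue to be followed every 3 months for a total of 2 years from the date of randomization". Calendar footnote 14 says the same. Section 12.5 gives 2 years, or a list of stopping points tied to the last enrolled subject, whichever is earliest. Section 12.6 asks that subjects who stop treatment for other reasons keep having tumour assessments on schedule until progression or death. Sections 8.8 and 12.6 censor at the last radiographic assessment.

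**Imaging.** Footnote 8: "A bone scan will be performed at baseline, C8D1 and after completion of 1 year of treatment". Section 7.8 lists no imaging for Cycles 14 to 16. Section 7.9, "Maintenance Cycle 17 Day 28", lists CT/MRI and no bone scan. Nothing is scheduled later. Section 7.7 labels C13D1 as "12 months from ADT initiation".

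**What counts.** Section 8: "RECIST 1.1 criteria will apply to only soft tissue lesions". Section 8.1.2 puts "Bone lesions, leptomeningeal disease, ascites, pleural/pericardial effusions" and other sites in the non-measurable class. Section 8.2.2 defines skeletal progression on bone scan, but also counts growth of a lesion's soft-tissue component on CT or MRI. Section 8.2.3 counts unequivocal progression of non-measurable disease and any new lesion.

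**Contingency.** Sections 12.1 and 12.3 permit, but do not require, extra enrolment if a blinded event count at 24 months projects well past month 48.

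**The concern.** The power calculation and the assessment schedule describe different trials. If rPFS cannot be observed for as long as 12.1 assumes, fewer events will be seen and the stated 90% is not what the design delivers.

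A second problem concerns description rather than testing. All eligible subjects have bone metastases, yet the test that defines skeletal progression is not scheduled after year 1. About a year separates C13D1 from C17D28. Section 12.6 still plans a Kaplan-Meier median and a 24-month rPFS proportion with no caveat. A reader could take a scan date for an estimated median, or take the figure at C17D28 to cover bone progression when the scheduled tests may not.

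**Working it through.** **1. Required events.** Schoenfeld, 1:2 allocation, one-sided alpha 0.10, power 0.90: (1.2816 + 1.2816)² / [(1/3)(2/3)(ln 0.632)²] = 140.4. With the exact ratio 12/19 it is 140.0. The plan's 140 reproduces.

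**2. Expected events under 12.1.** Monthly hazards are ln 2/12 = 0.05776 (control) and ln 2/19 = 0.03648 (radium). The dropout hazard g is -ln(0.9)/12 = 0.00878. The probability of an observed event within c months is

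λ/(λ+g) × [1 - exp(-(λ+g)c)].

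Averaged over c uniform on 24 to 48 months (everyone assessed to month 48), this is 0.780 and 0.640. Events: 68 × 0.780 + 136 × 0.640 = 53.1 + 87.1 = 140.1. Power is Φ(√(D × 2/9) × 0.4595 - 1.2816), with D the number of events, which gives 0.900. The plan's figures reproduce on this reading of follow-up.

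**3. Same inputs, follow-up as scheduled.** C13D1 is day 12 × 28 = 336 by cycle length. C17D28 is then day 336 + 4 × 84 + 27 = 699, or day 728 if C13D1 is day 365. Two years from randomization can reach about 25 months from first ADT dose, because ADT may start up to 28 days before registration.

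| Assessment per subject | P(event), control / radium | Events | Power | N for 140 events |
|---|---|---|---|---|
| Day 699 (23.0 months) | 0.680 / 0.521 | 46.2 + 70.9 = 117.1 | 0.856 | 244 |
| 24.0 months | 0.692 / 0.534 | 47.1 + 72.6 = 119.7 | 0.862 | 239 |
| 25.0 months | 0.704 / 0.546 | 47.8 + 74.3 = 122.1 | 0.867 | 234 |

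The last column is 204 × 140 / events. No input from outside the documents is used.

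**4. Adding the scan dates, nothing missed.** Simulation with progressions dated to the next attended scan and every progression visible at C17D28: about 113 to 116 events and power of about 0.85 to 0.87. Sparse scanning on common dates therefore costs little power by itself.

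**5. The gap and the median.** About 43 of the 117 events expected by day 699 fall between days 336 and 699. If all events are progressions and the C17D28 CT finds every one, the radium Kaplan-Meier median lands on that scan in about 93% of simulated trials and is not reached in the rest, against a true 19 months.

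**6. Sensitivity only; these rates are assumptions, not in the documents.** Suppose 10% of events are deaths, 30 to 70% of progressions are bone-only and not registered on CT at C17D28, and there are no prompted scans. Results over both timings of C13D1:
- 87 to 105 events, power about 0.77 to 0.83.
- Radium median between months 13 and 22.5 in at most 0.2% of trials. With 25, 50 or 75% of progressions found by prompted scans within 12 weeks, this becomes 2-4%, 15-22% and 51-56%.
- At 25 to 75% prompted: 94 to 114 events, power 0.79 to 0.86.
- Control median, no prompted scans: typically month 22 to 23 if C13D1 is day 336, but 12.0 if it is day 365. With 25 to 75% prompted: 13.1 to 14.7, or 12.0.
- rPFS at C17D28, 50% bone-only, no prompted scans: 36-38% control and 52-54% radium, against a truth of 25-27% and 42-43%. With 25 to 75% prompted, the excess is 2 to 9 points.

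**7. The 24-month projection.** The expected blinded count at month 24 is 72 under continuous detection, but 51 to 52 on the scan schedule (10% deaths, none prompted). A projection that ignores scan dates would misread the count.

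**The case against.** **12.5 is loosely worded.** It can be read as following everyone until the last subject reaches 24 months, which is month 48 and matches the synopsis. The 2-year limit in 7.10 is written for subjects who come off therapy, and 12.6 asks for continued assessment. The ambiguity is real. It does not rescue the 140: 12.6 continues assessments on schedule, the schedule ends at C17D28, and censoring is at the last scan. After that only deaths or unscheduled scans could add events.

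**Extra enrolment could make up the events.** It could, but it is optional and triggered by projected time, and it would not repair the median or the 24-month estimate.

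**The bone-only losses are assumed.** This stands. A reader might infer that power is really about 0.77 to 0.83. The documents do not support that as a finding: they give no rate of bone-only progression, and 8.1.2 with 8.2.3 allows bone lesions on CT to count. The loss shrinks if they count or if prompted scans occur.

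**Scan dates do not always set the median.** This also stands. At 75% prompted, about half of radium medians fall between scans. The documents leave room for such scans (contact for new pain, 12-weekly PSA, 8.2.4) without scheduling them. On the 12-month label, C13D1 also supports the 12-month estimate and the control median is typically close to its true value.

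**The log-rank test is not invalid.** A reader might infer bias from sparse scanning. The scheduled dates are the same in both arms, so the test remains valid as long as unscheduled scanning does not differ by arm.

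**Conclusion.** The point holds, and should be fixed. The arithmetic of 12.1 is sound, but it needs 24 to 48 months of rPFS assessment per subject, and the written schedule supplies about 23 to 25. On the documents' own inputs, expected events fall from 140 to about 117 to 122 and power from 0.90 to about 0.86 to 0.87. That loss is modest for a phase II trial at one-sided 0.10, and it comes from follow-up length, not from the missing bone scan.

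Separately, unless many progressions are found by unscheduled scans, the radium median will fall on a scan date or not be reached. rPFS at C17D28 will be too high to the extent that bone-only progression is missed. How far is unknown, because the documents give no rate and do not settle whether bone lesions on CT count.

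**What to change.** 1. **12.1, 12.3, 12.5, 7.10, footnote 14.** Reconcile the follow-up. Restate expected events and power for follow-up and imaging as written: about 117 to 122 events and 0.86 to 0.87, before any missed progressions. Base the blinded 24-month projection on the scan schedule, and say how the enrolment option would be used.
2. **12.6.** Keep the stratified log-rank test as primary. Report rPFS at the scheduled scan times. Add an interval-censored (grouped-time) hazard ratio as a sensitivity analysis; an unstratified version gave 0.63 to 0.65 in simulation against a true 0.632. State that the Kaplan-Meier median depends on scan dates.
3. **8, 8.1.2, 8.2.2, 8.2.3.** State whether bone lesions seen on CT/MRI after C13D1 count as rPFS events, and label the C17D28 figure accordingly.
4. **Calendar.** Reconcile the day-336 and 12-month timings of C13D1. Reconcile footnote 8, "CT and MRI scans if clinically indicated can be performed with or without intravenous contrast", with 7.5, 7.7 and 7.9, which list abdomen/pelvis CT/MRI without that condition. The footnote may mean only the chest and brain rows.

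The cost is protocol and SAP wording, a little programming and a less favourable stated power. If the enrolment option is used, more subjects are needed. No added visit or scan is required; whether to add imaging is for the sponsor to weigh.
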